### **Naltrexone Implant Procedure**

1. Naloxone Challenge - observe for signs of withdrawal
2. Local Anesthesia
  - a. Wash hands with antimicrobial soap
  - b. Apply antimicrobial handcream
  - c. Apply non-sterile gloves
  - d. Cleanse skin with antimicrobial wipe
  - e. Cleanse skin with isopropyl alcohol
  - f. Inject area with 2% lidocaine 5cc syringe with a 25g x S" needle under ~ 1" of skin
3. Pellet insertion
  - a. Apply antimicrobial handcream
  - b. Apply non-sterile gloves
  - c. Open packet of sterile supplies
  - d. Prepare Area with 3 sterile betadine swabs
  - e. Apply sterile gloves
  - f. Apply sterile drapes
  - g. Make ~1cm incision with sterile #15 scalpel
  - h. Inject 5cc of 2% lidocaine in 5cc syringe with a 18g x 1 S" needle through the wound in a medial direction anesthetizing a tract through which to insert the pellet insertion device.
  - i. Insert sterile pellet within sterile insertion device
  - j. Close wound with stitches

4. Clean and dress wound
5. Provide wound care instruction sheet to patient

### **Implantation Discharge Instructions**

1. Wash hands before touching site.
2. Keep clear dressing over pellet site for 24 hours.
3. Pull dressing off after 24 hours.
4. Clean with soap and water as usual in shower every day.
5. Make sure stitches stay dry - pat dry after shower.
6. Pour peroxide over stitches after shower.
7. Stitches will be removed when you return to Pavlov 7-11 days after implantation.

For redness or swelling in first 24 hours use ice. May use over the counter pain relievers such as Tylenol, Ibuprofen, Naproxen Sodium.

Bruising may occur on abdomen secondary to numbing medication administration.

If pellet site bleeds, hold pressure over site. Ice will also help stop bleeding at site.

If pellet site irritated during working hours - cover with band-aid during day - keep site open to air at night (No band-aid).

Notify office if fever develops, redness or swelling occur, or any discharge occurs.

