#### Procedures at Pavlov – Implantable Naltrexone and Naloxone Challenge

At this point the participant is started on study medication. Following CAH discharge, participants will come to PSMU to receive a 1000mg dissolvable naltrexone implant (IN). Participants will receive 4 naltrexone implants while in the study. Ideally, implants will be inserted every 10-12 weeks starting at week 4 post-study enrollment (weeks 4, 16, 28, 40), unless the participant relapsed. Relapse will be examined by self-report, evidence of fresh puncture marks, signs and symptoms of withdrawal or intoxication, and a urine drug screen that must be negative for opioids before receiving an implant. Participants will undergo a naloxone challenge at study visits during which the naltrexone implant is inserted and only if the participant's urine is opioid-free. If participant does not pass the naloxone challenge due to relapse, they will be referred to detox and will be invited to return upon completion of that treatment for a repeat naloxone challenge. Naltrexone implantation is an outpatient procedure to be conducted on site by a surgeon with the assistance of a study nurse. The implant will be inserted under the skin in the abdomen through a 1cm incision. The site will be treated with a local anesthetic prior to

insertion. The implant site will be inspected 7-11 days later when the participant returns for removal of sutures. Participants will receive discharge instructions to help care for the insertion site at home. Details on the procedure are presented at the end of this section.

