### Medication Risks

The most serious risk of naltrexone (both implant and injection) is the potential for hepatocellular injury when taken in excessive doses (the margin of separation between the apparently safe dose of naltrexone and the dose causing hepatic injury may be only five-fold or less). Harm is less likely at the dosage provided in this study. In alcohol dependence trials, liver enzymes that are initially elevated (likely due to excessive alcohol use) decreased in participants taking naltrexone. As a precaution, participants will have ALT and AST repeated at implant visits 2,3, and 4, and if either liver enzyme is >5 times the upper limit of normal, results will be shared with participant during their suture removal visit and a repeat test will be done during their next medication visit. If any repeat test result is again >5 times the upper limit of normal, or if a patient is symptomatic (e.g. fatigue, anorexia, jaundice, nausea, vomiting, dark urine, light stool, abnormal pain), the patient will be referred to a hepatologist for further evaluation and a recommendation about continuing study medication. We expect this situation to be rare or non-existent based on prior experience with naltrexone. These precautions, combined with frequent contact with study staff, will provide thorough monitoring and appropriate response if evidence of liver damage emerges in the course of the study.

Normal ranges:

AST: Male: to 38 units/L; Female: to 32 units/L

ALT: Male: to 41 units/ L; Female: to 31 units/L

Exposure to naltrexone can precipitate severe withdrawal if the participant is physiologically dependent on opioids. To avoid unintended withdrawal, participants will be given a naloxone challenge prior to starting naltrexone, as described earlier.

Though data from the Lucey et al study (2008) using injectable naltrexone showed no effect of nonsteroidal anti-inflammatory drugs (NSAIDs) in patients taking naltrexone, other studies have shown that non-steroidals taken with naltrexone can increase the chances of liver damage. As a precaution, participants will be warned of this possibility and advised to take NSAIDs only if necessary, and to take low doses if use of these medications is necessary. Non-steroidal use will be recorded so that the potential for such interactions can be evaluated.

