2. AST, ALT
  - a. AST/ALT will be measured only among intervention participants during implant visits 2, 3, and 4 to assess liver toxicity.
3. HIV Antibody Test
  - a. If a participant has an undetectable HIV viral load at baseline, an HIV antibody test will be conducted during their next study visit to verify their HIV status.

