## 6.2 THE METHODS AND TIME FOR ASSESSING, RECORDING, AND ANALYZING SAFETY PARAMETERS

- For participants randomized to the LINC-II intervention, symptoms will be assessed at baseline to document any chronic conditions or symptoms that existed prior to introduction of study medication. These will be documented on the Baseline AE log. This list will be reviewed and compared to reported events throughout the study. *If the participant reports the same ongoing symptom (same severity) during subsequent visits, the symptom should not be recorded as an Adverse Event (AE). If the event is new (not previously reported) or worsened, as determined by RA, then it will be considered an AE and recorded and reported as described below.*
- During each scheduled visit, the RA will ask the participant how he or she feels and review the previously reported symptoms. Any event that meets the above criteria for an AE/SAE/UP must be recorded. In the case of unresolved AEs, clinical staff will update the AE log with any follow-up information that is gathered during their investigation.
- The site will receive the results of all blood work that is performed on study participants from the designated lab. If the lab results meet the criteria described in the protocol as an AE and are considered clinically significant by the site clinician then an AE will be recorded.
  - Participants will be alerted of abnormal lab results and will receive a recommendation to see their local provider (please see section 3.3C for protocol specific to AST/ALT results). All abnormal lab results obtained at the baseline visit will be listed on the Baseline AE log. During follow-up visits, abnormal lab results will be listed as an AE only if the abnormal lab results meet one of the points below:
    - Develop at follow-up (i.e., were not previously recorded at baseline).
    - Worsen in severity compared to what was previously recorded at baseline.
    - Or are considered clinically significant.
  - All AEs will be assessed to determine if they meet criteria for a Serious Adverse Event (SAE). If the AE is serious, then the SAE form must be completed and appropriate reporting measures followed (see below). Investigators are encouraged to consult with the US team, if they are uncertain how to classify an event.
  - The list of participant's current medications will be reviewed and updated at every study visit, starting at baseline.

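### The implant discharge sheet allows over-the-counter ibuprofen and naproxen without the NSAID precaution that the protocol sets out under Medication Risks

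*Combined protocol and SAP*

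**What the plan says.** Section 3.3.C, Medication Risks, discusses NSAIDs and naltrexone together. It cites one study of injectable naltrexone that found no NSAID effect, then adds that "other studies have shown that non-steroidals taken with naltrexone can increase the chances of liver damage". Its response is precautionary: "participants will be warned of this possibility and advised to take NSAIDs only if necessary, and to take low doses". It also undertakes to record NSAID use so that an interaction can be examined.

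Later in the same section, the Implantation Discharge Instructions tell the participant: "May use over the counter pain relievers such as Tylenol, Ibuprofen, Naproxen Sodium". No other line of that sheet mentions the liver, dose or need.

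The sheet is for participants. The text on procedures at Pavlov says: "Participants will receive discharge instructions to help care for the insertion site at home". The last step of the Naltrexone Implant Procedure is: "Provide wound care instruction sheet to patient".

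On liver monitoring, section 3.7.B says: "AST/ALT will be measured only among intervention participants during implant visits 2, 3, and 4 to assess liver toxicity". On concomitant medication, section 6.2 says that the participant's "current medications will be reviewed and updated at every study visit, starting at baseline".

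**The concern.** The protocol identifies a possible hazard and chooses a precaution, but the written advice that the participant carries home after minor surgery leaves it out. The sheet puts ibuprofen and naproxen sodium on the same footing as Tylenol. A participant who follows it as written gets less cautious advice than the protocol intends, just after an incision and stitches, when pain relief may well be wanted.

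What is at stake is participant safety, and only modestly. Medication Risks names hepatocellular injury at excessive doses as the most serious risk of naltrexone. Entry excludes only ALT or AST above five times the upper limit of normal and known liver failure (section 2.7), so people with lesser enzyme elevations can receive implants. The scheduled liver tests would pick up a problem only some weeks later, or not at all after the last implant.

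**Working it through.** The plan states no figure on this point, so the check compares two texts and then looks at timing.

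**1. The two texts, element by element**

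| Element of the precaution (Medication Risks) | On the discharge sheet? |
|---|---|
| Warning about possible liver damage with naltrexone | No |
| NSAIDs only when needed | No |
| Low doses | No |

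The sheet carries 0 of 3 elements, and 2 of the 3 products it names are NSAIDs. The 24-hour limit just before the sentence belongs to the use of ice for redness or swelling. The pain-reliever sentence has no time limit of its own, although short-term use is probably what is meant.

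**2. How often the sheet is used**

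- Intervention arm: 120 (section 2.4).
- Implants per participant: 4, ideally at weeks 4, 16, 28 and 40 (sections 2.4 and 3.3.C).
- Ceiling on hand-outs: 120 x 4 = 480.

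The true number will be lower, because relapse or a failed naloxone challenge blocks implantation. It counts sheets, not NSAID exposures or liver events.

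**3. Time from each sheet to the next scheduled ALT/AST**

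Tests are drawn at implant visits 2, 3 and 4, that is, weeks 16, 28 and 40 on the ideal schedule.

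- Sheet 1: 16 - 4 = 12 weeks.
- Sheet 2: 28 - 16 = 12 weeks.
- Sheet 3: 40 - 28 = 12 weeks.
- Sheet 4: no later test is scheduled; 52 - 40 = 12 weeks of follow-up remain.

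With the stated implant spacing of 10-12 weeks, the first three gaps are 10-12 weeks. Section 3.6.A also expects early and late visits, so individual gaps may differ. The exceptions are in Medication Risks: a result above five times the upper limit is repeated at the next medication visit, and symptoms lead to referral to a hepatologist.

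**4. What is not affected**

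NSAID use is still captured, because medications are reviewed at every study visit. Nothing here enters the sample size, the primary outcome or its analysis.

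**The case against.** The strongest reply is that the plan already deals with this. Medication Risks commits staff to give the warning and does not say through which document. The handout concerns wound care, and nothing requires it to carry drug-interaction advice. The same section uses the consent form to explain overdose risk, and participants receive a copy of that form (section 4.3). Its pages are not in the copy reviewed, so the NSAID warning may already be with participants in writing. This stands as a limit: the precaution is missing from the sheet, not shown to be missing from the trial. It does not explain why a later handout should name NSAIDs as acceptable without the caution.

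A second reply is that the exposure is small and watched. The sentence is permissive, covers only over-the-counter products and lists Tylenol first, and Medication Risks puts local irritation at 2-3 days. Participants return 7-11 days after each implant for suture removal, and symptoms are checked every four weeks (section 3.5.A). This also stands, and it is why the point is minor. Those visits can detect harm, however; they do not replace advice meant to prevent it. No figure shows how many participants would take a pain reliever.

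A third reply is that the ALT/AST draws monitor naltrexone, so setting a 12-week interval against a few days of analgesic use proves no risk. That is fair. The interval shows only that scheduled testing is not a close backstop.

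**Conclusion.** The concern holds as a minor one. The discharge sheet omits all three parts of a precaution that the protocol itself adopts; this is an omission and not a contradiction.

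Confidence is high in the comparison of the texts, but not in any clinical consequence. The documents give no rate of NSAID use or of liver events, the evidence they describe is mixed, and they consider harm less likely at the study dosage. The clinical effect is therefore not quantified and is probably small.

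The conclusion assumes that the wound care sheet in the implant procedure is the set of Implantation Discharge Instructions printed in section 3.3.C, which is the natural reading. It makes no assumption about what staff say or what the consent form contains.

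**What to change.** Replace the pain-reliever sentence in the Implantation Discharge Instructions with, for example: *For pain, Tylenol may be used as directed on the label. Take ibuprofen or naproxen only if necessary and at a low dose, because with naltrexone they may raise the chance of liver damage. Tell study staff if you use them.*

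The NSAID advice follows Medication Risks. The Tylenol clause adds only a label limit to something the sheet already permits. The last sentence supports the existing commitment to record NSAID use.

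The cost is the rewording, Russian translation and IRB approval of one entry on one participant sheet. Visits, laboratory tests, data collection and analysis stay as they are.

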### **Counseling**

Assessors will administer brief counseling (~5 minutes) to participants during the medication visits. The brief counseling will be conducted by study RAs (addiction psychiatrists) based on standard clinical protocols.

### **3.4 CONTROL GROUP**

Participants in the control group will receive standard care as normally provided to patients in the narcology hospital. This could include detoxification with medications, substance use counseling and treatment for comorbid psychiatric conditions, as well as possible inpatient rehabilitation for up to 30 days. They will also be given printed information, including phone numbers, on places that provide HIV medical care and will be referred to outpatient narcology care. Detoxification takes 5-7 days, most commonly using clonidine, antidepressants, non-opioid analgesics, hypnotics, and Imodium. Stabilization occurs within the same ward, takes 1-2 additional weeks, and includes drug counseling and treatment of comorbid psychiatric problems. Upon hospital admission, HIV testing is routinely performed in all patients who are not documented to be HIV-positive. Prior to discharge, those identified as HIV-positive

are given contact details for an HIV clinic, not an appointment. Upon discharge, patients are encouraged to receive outpatient narcology treatment, monthly, for 1 year. If control participants are newly diagnosed with HIV infection at the CAH, they will receive HIV post-test counseling consistent with CDC recommendations. Participants who visit the AIDS center will be able to receive ART medication provided they undergo required pre-ART testing and examinations. Enrollment in the study will not preclude participants from receiving any HIV or narcology care that would normally be accessible to them.

### **3.5 MEDICATION CONSIDERATIONS**

#### **3.5.A SYMPTOM MONITORING**

The study staff (research clinicians [addiction physicians with extensive experience performing pharmacotherapy trials]) have extensive experience administering implantable and injectable naltrexone, and specimen collection via prior OUD pharmacotherapy studies. They will be trained to assess for adverse medication effects and will follow established protocols for identifying and monitoring any ongoing adverse events, including referral to treatment as appropriate. Study participants will be actively monitored for adverse events. Symptoms will be monitored every four weeks (and more frequently, if necessary) by trained clinical staff, while the participants are administered study medications.

#### **3.5.B. DISCONTINUATION OF STUDY MEDICATION**

Despite known side effects of naltrexone (both implant and injectable), most people taking the medications do not discontinue them due to side effects. Those who discontinue medication will be followed and analyzed by intention to treat.

Participants found to be pregnant during the study will have their study medication (i.e., naltrexone) discontinued (including removal of the implant if necessary), but will still be followed-up for the duration of the study. Participants who report pregnancy outside of study visits will be requested to come to Pavlov for a confirmatory pregnancy test where the need for implant removal will be assessed and the implant may be removed if deemed necessary.

### **3.6 SCHEDULE OF DATA COLLECTION**

Intervention Group								
		Pre-screen	Screener and Baseline	Implant visits	Medication Checks (every 4 weeks post implant)	6-month visit (24 weeks)	12 month visit (52 weeks)	

			Screener	Baseline			
Screening	Verification of HIV, pregnancy, AST/ALT	X					
	Screening Questions		X				
Enrollment	Sign Informed Consent		X				
	Complete contact information/verify numbers			X			
	Randomization			X			
Laboratory	Clinical Values			X	X	X	X
	Pregnancy Test		X		X	X	X
	Urine Drug Test			X	X	X	X
	CD4			X		X	X
	HVL			X		X	X
	ALT/AST				X		
Assessment	Full Study Assessment			X		X	X
	Qualitative Assessment			X		X	X
	Medical Record Review	X				X	X
Intervention	Symptom Management/Adverse Events			X	X	X	X
	Naloxone challenge			X	X		
	Naltrexone Injection			X			
	Naltrexone Implant				X		
	Brief Counseling				X	X	X
Other	Compensate for Participation			X	X	X	X
	Provide Resource Card			X			
	Report Adverse Events			X	X	X	X
	Complete Tracking Forms			X	X	X	X

Control Group						
		Pre-screen	Screener and Baseline Visit		6 mo (24 weeks)	12 mo (52 weeks)
			Screener	Baseline		
Screening	Verification of HIV, pregnancy, AST/ALT	X				
	Screening Questions		X			
Enrollment	Sign Informed Consent		X			
	Complete contact information/verify numbers			X		
	Randomization			X		
Laboratory	Clinical Values			X	X	X
	Pregnancy Test		X			
	Urine drug Test				X	X
	CD4			X	X	X
	HVL			X	X	X
Assessment	Full Study Assessment			X	X	X
	Qualitative Assessment			X	X	X
	Medical Record Review	X			X	X
Other	Provide Resource Card			X		
	Compensate for Participation			X	X	X
	Complete Tracking Forms			X	X	X

### 3.6.A. VISIT WINDOWS

#### Research Assessment Windows for Intervention and Control Group

##### 6 Month (24-week) Visit

- Window open: 120 days post baseline
- Target date: 180 days post baseline
- Window close: 270 days post baseline
- Window length: 150 days

[figure not shown]
##### 12 Month (52-week) Visit

- Window open: 271 days post baseline
- Target date: 365 days post baseline
- Window close: 455 days post baseline
- Window length: 184 days

#### Intervention Group Medication Visit Windows

Implant visits will take place 10-12 weeks apart starting with week 4. Ideally, implant visits will occur 4, 16, 28, and 40 weeks post enrollment, but we will accommodate the following windows.

## Naltrexone Implant Windows

### Study Timeline

(52 Weeks)

Medication visits will take place every 4 weeks following the implant visit, with ideally 2 medication visits after each implant

Windows listed above are used as guides for scheduling visits, but early/late visits are expected due to participant/laboratory scheduling.

## 3.7 DATA SOURCES

### 3.7.A QUESTIONNAIRES

Questionnaires will be administered at baseline, 6-, and 12-month study visits to collect information about participant demographics (e.g., age, gender), general and mental health and health-related behaviors such as substance use.

Questionnaires for providers are described in section 5.3 SYSTEM-LEVEL ASSESSMENT OF LINC-II IMPACT.

### 3.7.B. BLOOD

Blood will be collected at baseline, implant visit 2, 3, and 4, and 24 and 52 weeks to assess the following:

1. CD4, HIV-1 RNA
  - a. Measured at baseline, 24- and 52-week study visits among control and intervention participants. Samples collected at City Addiction Hospital (baseline) and Pavlov University (follow-up) are sent to the City AIDS Center for testing. Results from the testing are placed in participant medical records at City AIDS Center and provided to the Pavlov University research team.

- i. If CD4 and HVL results are already available at the City AIDS Center within the 24- and 52-week visit windows, a new study test will not be conducted and existing results will be used.
  - ii. If recent (within one month) CD4 and HVL results are available at the City AIDS Center, a new baseline study test will not be conducted and existing results will be used.
  - iii. If a participant is unable to provide blood during their 6 or 12 month study visit and does not have a blood draw scheduled at the City AIDS Center within the study visit window, we will take the following approach:
    1. Control group: Participant will be invited to come in for a second blood draw attempt in 4 weeks. Participants will receive compensation in the amount of 500 rubles to cover costs associated with traveling to the laboratory.
    2. Intervention group: A second attempt at a blood draw will be made in 4 weeks (at their scheduled 28 week medication visit or after the completion of the 12 month visit). At the 28-week visit, participants will receive planned compensation for attending the medication visit but will not receive additional compensation for the blood draw. For the second attempt after the 12 month visit, participants will receive compensation in the amount of 500 rubles to cover costs associated with traveling to the laboratory.
  - iv. If a participant is unable to provide blood during their 6- or 12-month study visit due to COVID-19 restrictions and does not have a blood draw scheduled at the City AIDS Center within the study visit window, we will take the following approach:
    1. Control group: Participants will be invited back to Pavlov for a blood draw once restrictions are lifted. Participants will receive compensation in the amount of 500 rubles to cover costs associated with traveling to the laboratory.
    2. Intervention group: A blood draw attempt may be made during a medication check-in visit, if one is scheduled. In which case, participants will receive planned compensation for attending the medication visit but will not receive additional compensation for the blood draw. If a blood draw does not take place during a scheduled medication visit, or if no visit is scheduled, participants will be invited to come to Pavlov once restrictions are lifted. For the blood draw attempt outside of their scheduled visit, participants will receive compensation in the amount of 500 rubles to cover costs associated with traveling to the laboratory.
  - v. If CD4 and HVL results are available in participant's medical chart at the CAC, we will enter them as part of the Chart Review process.

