### 2.3 STUDY OUTCOMES

[figure not shown]
**Aim 1.** The primary outcome for aim 1 is defined as an undetectable HVL at 12 months post randomization, assessed by study test within a window of 9–15 months. Secondary outcomes are initiation of ART within 28 days of randomization, change in CD4 count between baseline and 12 months (assessed by study test), retention in HIV care (at least 1 visit to medical care in 2 consecutive 6 month periods within 12 months of enrollment, assessed by medical record review and by self-report), undetectable HVL at 6 months post randomization assessed by study test, and a composite outcome for achieving both HVL suppression and past 30-day opioid abstinence assessed at 6 and 12 months.

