#### **Intervention Group:**

- At the **medication visits**, the Pavlov RA will perform the following:
  - Review and update locator/contact information, verifying new numbers, as necessary
  - Collect a urine sample to check for pregnancy and conduct drug testing
  - Collect clinical data (weight, blood pressure)
  - Assess opioid use
  - Perform symptom monitoring (including inspection of implant site) and brief counseling
  - Compensate participant and schedule next visit
- In addition to the above, at the **implant visits**, the Pavlov RA will perform the following:
  - Administer naloxone challenge
  - Provide naltrexone implant
  - Implant visits 2, 3, and 4: send participant for phlebotomy to check ALT/AST levels
- During the **24-, and 52-week assessments**, in addition to the medication visit procedures described above, the Pavlov RA will:
  - Send participant for phlebotomy (CD4, HVL)
  - Administer assessment questionnaire
  - **Subset of all participants:** In-depth interview

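### Does using an existing City AIDS Center result in place of the scheduled blood draw undermine the viral-load and CD4 outcomes?

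*Combined protocol and SAP*

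**What the plan says.** Section 2.3 gives the primary outcome as undetectable HVL at 12 months, "assessed by study test within a window of 9–15 months". Two secondary outcomes carry the same qualifier: CD4 change from baseline to 12 months, and "undetectable HVL at 6 months post randomization assessed by study test". Section 4.4 lists the CD4/HVL draw among the week-24 and week-52 procedures in both arms and mentions no exception.

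Section 3.7.B item 1.a.i supplies one. If City AIDS Center results are on file "within the 24- and 52-week visit windows, a new study test will not be conducted and existing results will be used". Item ii does the same at baseline for a result no more than a month old. Items iii and iv arrange a further attempt after a failed or COVID-prevented draw, but only if no City AIDS Center draw is scheduled in the window. Item v enters City AIDS Center results from the chart and does not say what part they play in the analysis.

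Section 3.6.A sets the windows. At 6 months: "Window open: 120 days post baseline" and "Window close: 270 days post baseline", with target day 180. At 12 months: "Window open: 271 days post baseline", with target day 365 and close at day 455. Section 8.1 specifies logistic regression adjusted for ever ART use. It does not name a result source or a way to choose among results.

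**The concern.** Section 2.3 appears to choose its sources on purpose, because in the same paragraph it assigns retention to records and self-report. Item i itself contrasts a new study test with existing results. Read literally, the primary value for some participants is therefore not the measurement that section 2.3 names.

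The substitution also depends on events after randomization. An existing result is available only for someone tested in care, and it is older than the draw it replaces. Case management is meant to increase HIV care (section 3.3.A), and section 3.3.B has the case manager schedule City AIDS Center visits, while controls receive contact details without an appointment (section 3.4). If substitution were commoner in one arm, and older results differed systematically from fresh ones, part of the arm difference could come from the timing of measurement. Separately, a long window can hold several results, and a binary endpoint can turn on which one is taken.

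**Working it through.** **1. The plan's own figures.**
- Window lengths: 270 − 120 = 150 days and 455 − 271 = 184 days, both as stated in section 3.6.A.
- In months of 30.4375 days, the 12-month window runs from 271/30.4375 = 8.9 to 455/30.4375 = 14.9, which agrees with the 9 to 15 months in section 2.3.
- Power (section 2.8.A): 27% vs 10%, 96 evaluable per arm, alpha 0.05 taken as two-sided, continuity correction 1/96. The pooled rate is 0.185. The null SE is √(0.185 × 0.815 × 2/96) = 0.0560 and the alternative SE is √((0.10 × 0.90 + 0.27 × 0.73)/96) = 0.0547. Power = Φ[(0.17 − 0.0104 − 1.96 × 0.0560)/0.0547] = Φ(0.91) = 0.818, against 80% stated. The substitution rule changes none of these inputs.

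**2. How old can a substituted result be?** Maximum lead over the draw it replaces = visit day − window-open day.
- 12 months, visit on target: 365 − 271 = 94 days. Visit at window close: 455 − 271 = 184 days.
- 6 months, visit on target: 180 − 120 = 60 days. Visit at window close: 270 − 120 = 150 days.

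**3. Does that widen what is accepted?** No. A study draw may fall from 94 days before to 90 days after the 12-month target (271 − 365 = −94; 455 − 365 = +90), and from 60 days before to 90 days after the 6-month target. Every date open to a substitute is open to a study draw. A participant seen on day 450 whose chart holds a day-370 result is measured closer to target by substitution.

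**4. Are the two measurements of the same kind?** Sections 2.5 and 3.7.B send study samples to the City AIDS Center for testing, and the study results are filed in the participant's record there. The laboratory is the same and the window is the same. The rule has no arm condition.

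**5. Which result counts?** With a single existing result, item i answers: it is used. The question stays open only when several City AIDS Center results share a window, or when a study result and a City AIDS Center result are both present.

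**6. What would a bias require?** To first order, with no true effect, the spurious difference = (substituted share, intervention − substituted share, control) × shift in the undetectable rate caused by source or timing. The documents give none of these quantities. Purely as assumptions:
- Shares of 50% vs 20% and a 5-point shift: 0.30 × 5 = 1.5 points.
- Shares of 70% vs 20% and a 10-point shift: 0.50 × 10 = 5.0 points.
- Equal shares: 0.

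The planned difference is 17 points. The range of 0 to 5 points only restates the assumptions. Nothing in the documents indicates the shares, the shift or its sign.

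**The case for a change.** The best case for a change is that the primary endpoint is binary, its source partly follows post-randomization care, and a remedy looks cheap: draw blood from every attender, prefer that result, and fall back on the chart only when there is no draw. The visits and the chart review are already planned. The issue also reaches further than follow-up HVL. Item ii can replace the baseline CD4, so both ends of CD4 change may come from the chart, and the composite outcome could pair an older HVL with a later report of 30-day opioid abstinence.

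Part of this stands. Sections 2.3 and 3.7.B do not use the same words, and there is no tie-break for several in-window results.

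The case for a compulsory repeat draw does not stand. The waiver is deliberate and consistent: items i to iv and the compensation rules in section 4.6 all treat an in-window City AIDS Center draw as sufficient. Reversing it adds assays and venepuncture in people who inject drugs, a group for whom the protocol already plans for failed draws. It would not remove the dependence on care either, because people without a study draw would still be classified from care records. Draws already waived could not be recovered, so if the trial is under way the source could vary with calendar time. It would also leave baseline substitution as it is, and it would not say how the redraw triggers in items iii and iv should then work.

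**Conclusion.** No change is called for. Followed as written, the plan gives a sound endpoint: one laboratory, one declared window per time point and one rule for both arms. The difference in wording is between a summary of outcomes and the section that governs blood collection. The more specific section states its exception openly, and section 4.4 is a visit checklist that omits the other draw contingencies too. The missing tie-break is a detail that a competent analyst fills by applying a single rule to both arms, such as taking the result nearest to target, with the source and date of each value kept. Repeat draws for attenders are a fair trade-off that the sponsor has resolved the other way.

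In size, a substituted result can be at most 94 or 184 days older than the draw it replaces at 12 months (visit on target or at window close), and 60 or 150 days at 6 months. All of these dates lie inside windows that already apply to study draws. This conclusion assumes that substitution is applied alike in both arms, as the text says, and that the choice among several results does not depend on their values. How often substitution occurs, and whether it differs by arm, cannot be known from the documents.
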